5. STUDY TREATMENTS

5.1. Investigational Product and Reference Therapy

The contents of the label will be in accordance with all applicable regulatory requirements.

Under normal conditions of handling and administration, investigational product is not expected to pose significant safety risks to site staff. Take adequate precautions to avoid direct eye or skin contact and the generation of aerosols or mists. Notify the monitor of any unintentional occupational exposure. A Material Safety Data Sheet (MSDS) describing the occupational hazards and recommended handling precautions will be provided to site staff if required by local laws or will otherwise be available from Novartis upon request. Adequate precautions must be taken to avoid direct contact with the investigational product.

Investigational product must be stored in a secure area under the appropriate physical conditions for the product. Access to and administration of the investigational product will be limited to the investigator and authorized site staff. Investigational product must be dispensed or administered only to subjects enrolled in the study and in accordance with the protocol.

Please refer to the SPM for detailed instructions related to:

- storage conditions
- infusion preparation
- premedication
- dosing schedule
- handling of infusion reactions
- observations required during infusions

5.1.1. Ofatumumab

The investigational medical product, ofatumumab, is a clear liquid concentrate for solution for infusion presented in glass vials. Ofatumumab will be infused intravenously on day 1 (300mg) and day 8 (1000mg) in the first cycle, followed by infusions of 1000mg every 2 months.

The ofatumumab infusions will be prepared in 1000 mL sterile, pyrogen free 0.9% NaCl to yield a 0.3 mg/mL and 1 mg/mL ofatumumab concentration for the first and subsequent infusions, respectively. Please refer to the SPM for instruction correct preparation of the investigational medical product.

5.1.1.1. Ofatumumab Pre-Medication

Pre-medication before each ofatumumab infusion must be given within 30 minutes to 2 hours prior to the treatment as detailed in Table 1:

Table 1 Pre-medication Requirements prior to Ofatumumab Infusions

Infusion #	Acetaminophen (po) or equivalent	Antihistamine (iv or po) diphenhydramine or equivalent	Glucocorticoid (iv) prednisolone or equivalent ¹
1st	1000 mg	50 mg	50 mg
2nd	1000 mg	50 mg	50 mg
3rd -Nth	1000 mg	50 mg	0 – 50 mg ²

^{1.} Please refer to the SPM for glucocorticoid equivalent doses.

^{2.} If the 2nd infusion has been completed without the subject experiencing any grade = 3 AEs, pre-medication with glucocorticoid may be reduced or omitted before the 3rd to Nth infusion at the discretion of the investigator.

5.1.1.2. Ofatumumab Treatment Schedule

Please refer to the study procedures manual for the preparation of the ofatumumab infusion.

First Infusion of 300mg Ofatumumab

The initial rate of the first infusion of 300mg ofatumumab (0.3mg/mL) should be 12mL/hour (hr). If no infusion reactions occur the infusion rate should be increased every 30 minutes, to a maximum of 400 mL/hr, according to Table 2. If this schedule is followed, the infusion duration will be approximately 4.5 hours.

Table 2 Infusion rate at 1st Ofatumumab (300 mg) infusion

Time	mL/hour
0 – 30 minutes	12
31 – 60 minutes	25
61 – 90 minutes	50
91 – 120 minutes	100
121 - 150 minutes	200
151 - 180 minutes	300
181+ minutes	400

If an infusion reaction develops, the infusion should be temporarily slowed or interrupted. Upon restart, the infusion rate should be half of the infusion rate at the time the infusion was paused. If, however, the infusion rate was 12 mL/hr before the pause, the infusion should be restarted at 12 mL/hour. Hereafter, the infusion rate may be increased according to the judgment of the investigator, in the manner described in this section.

Subsequent infusions of 1000mg Ofatumumab

If the previous infusion has been completed without grade ≥ 3 infusion-associated AEs, the subsequent infusion of 1000 mg (1mg/mL) can start at a rate of 25 mL/hr and should be doubled every 30 minutes up to a maximum of 400 mL/h, according to Table 3. Duration of the infusion will be approximately 4 hours if this schedule is followed. If the previous infusion has been completed with grade ≥ 3 infusion associated AEs, the subsequent infusion should start at a rate of 12 mL/hour according to Table 2.

Table 3 Infusion rate at subsequent Ofatumumab (1000 mg) infusion

Time	mL/hour
0 – 30 minutes	25
31 – 60 minutes	50
61 – 90 minutes	100
91 – 120 minutes	200
121+ minutes	400

Subsequent infusions=2nd and 3-14th infusions

During infusion the patient should be monitored closely and appropriate measurements should be performed whenever judged necessary. For details please refer to the SPM.

Dose reductions or modifications of ofatumumab are not permitted with the exception of those initiated for patient safety (i.e. due to infusion reactions). If a dose delay is required for ofatumumab, due to but not limited to adverse events, dosing may resume at physician discretion, and if the patient is still considered to be in remission.

5.1.1.3. Management of Infusion Reactions

5.1.1.3.1. Mild and Moderate Intensity Adverse Events (Grade 1 and 2)

If the investigator judges the AE to be related to the infusion, the infusion may be temporarily slowed or interrupted.

When the subject's condition is stable, the infusion can be restarted according to the judgment of the investigator.

Upon restart, the infusion rate should be half of the infusion rate at the time the infusion was paused. If, however, the infusion rate was 12mL/hr before the pause, the infusion should be restarted at 12mL/hr.

Hereafter, the infusion rate may be increased according to the judgment of the investigator, in the manner described in Table 2 and Table 3 (i.e. not more than doubled and no earlier than every 30 minutes).

5.1.1.3.2. Severe Intensity Adverse Events (Grade ≥ 3)

If the investigator judges a grade ≥ 3 AE to be related to the infusion, the infusion must be interrupted and the appropriate clinical intervention begun. When the AE decreases to grade <3 , the investigator may restart the infusion.

Upon restarting the infusion, the infusion rate must be 12mL/hr for the first infusion or 25mL/hr for subsequent infusions, and may subsequently be increased according to the judgment of the investigator, as described in Table 2 and Table 3 (i.e. not more than doubled and no earlier than every 30 minutes).

If the severity of the AE does not resolve to grade <3 despite adequate clinical intervention, or the same AE increases to grade $=3$ on three occasions during one infusion, the subject should be withdrawn from treatment.

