6.4.6. Laboratory and Other Safety Assessment Abnormalities Reported as AEs and SAEs

Any abnormal laboratory test results (hematology, clinical chemistry, or urinalysis) or other safety assessments (e.g., ECGs, vital signs measurements), including those that worsen from baseline, and felt to be clinically significant in the medical and scientific judgement of the investigator are to be recorded as AEs or SAEs.

However, any clinically significant safety assessments that are associated with the underlying disease, unless judged by the investigator to be more severe than expected for the subject's condition, are **not** to be reported as AEs or SAEs.

B cell depletion, IgG below LLN, low CD19+ count, and hypogammaglobulinemia due to treatment with ofatumumab are **not** to be reported as AEs or SAEs.

Infusion related AEs may lead to a prolonged infusion time. Overnight stay at the hospital due to slow infusion rate is **not** to be reported as a SAE.

Specific attention will be paid to monitor events of special interest such as infusion reactions, tumor lysis syndrome, infections and progressive multifocal leukoencephalopathy (PML). Please refer to the SPM and/or the following text*.

Handling Infusion Reactions:

Infusion reactions are commonly associated with anti-CD20 antibody therapy. Ofatumumab can cause serious infusion reactions manifesting as bronchospasm, dyspnea, laryngeal edema, pulmonary edema, flushing, hypertension, hypotension, syncope, cardiac ischemia/infarction, back pain, abdominal pain, pyrexia, rash, urticaria, and angioedema. Infusion reactions occur more frequently with the first 2 infusions.

The site staff must be prepared to intervene if an infusion reaction occurs. Special caution should be taken during the first infusion for each subject and during the infusion for any subject who did not tolerate a previous infusion well. It is recommended that a crash cart is readily accessible in the event of an emergency. Infusion reactions should be treated according to the investigators judgment and best clinical practice.

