Interruption, restart and increasing the rate of the infusion depending on the severity of the AE must be according to the description below and at the investigator's discretion. An increase of the infusion rate after an interruption must not exceed the scheduled amount as described in Table 2 and Table 3 (i.e. not more than doubled rate and no earlier than every 30 minutes). See Section 5.1.1.3 for details on management related to intensity of adverse events.

Handling Tumor Lysis Syndrome:

Monitoring and treatment of potential Tumor Lysis Syndrome (TLS) should be performed as per oncology standard of care.

Symptoms of TLS include:

- Hyperkalemia, potentially leading to cardiac conduction abnormalities, muscle weakness or paralysis
- Hyperphosphatemia, potentially leading to renal failure
- Hypocalcemia. Symptoms include (but are not limited to): tetany, seizures, mental retardation / dementia, parkinsonian (extrapyramidal) movement disorders, papilledema, emotional instability / agitation / anxiety, myopathy
- Hyperuricemia, potentially leading to renal failure

Risk factors for TLS include a high tumor burden, high concentrations of circulating cells ($\geq 25,000/\text{mm}^3$), hypovolemia, renal insufficiency, elevated pre-treatment uric acid levels and elevated lactate dehydrogenase levels. Thus TLS should be suspected in subjects with large tumor burden who develop acute renal failure along with hyperuricemia ($> 15 \text{ mg/dL}$) or hyperphosphatemia ($> 8 \text{ mg/dL}$). Acute uric acid nephropathy is associated with little or no urine output. The urinalysis may show uric acid crystals or amorphous urates. The hypersecretion of uric acid can be detected with a high urine uric acid:creatinine ratio > 1.0 , compared to a value of 0.6-0.7 for most other causes of acute renal failure.

In those patients considered to be at risk for TLS, management includes correction of electrolyte abnormalities, monitoring of renal function, maintenance of fluid balance (consider aggressive hydration i.e. $\sim 3,000 \text{ ml/m}^2/\text{day}$ fluid administered parenterally) and supportive care. If signs of TLS occur, the investigator can administer rasburicase or allopurinol (e.g. Zyloprim, Allohexal, Allosig, Prologon, Zyloric) or other drugs used to treat hyperuricemia, per prescribing information, if deemed appropriate.

Handling Progressive multifocal leukoencephalopathy (PML):

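### The restart rate after a grade 3 or higher infusion reaction overlooks later infusions that were deliberately started at 12 mL/hr

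*Protocol*

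**What the plan says.** Protocol Section 5.1.1.2 gives a subsequent infusion (defined under Table 3 as the second to the fourteenth) one of two starting rates. If the previous infusion passed without a grade 3 or higher infusion-associated event, it can begin at 25 mL/hr and follow Table 3. If there was such an event, "the subsequent infusion should start at a rate of 12 mL/hour according to Table 2".

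Section 5.1.1.3 then deals with reactions during an infusion, by grade. For grade 1–2, Section 5.1.1.3.1 halves the rate on restart and protects the lowest rate: if "the infusion rate was 12mL/hr before the pause, the infusion should be restarted at 12mL/hr". For grade 3 or higher, Section 5.1.1.3.2 makes interruption mandatory, leaves it to the investigator whether to restart once the event has fallen below grade 3, and fixes the restart rate: "the infusion rate must be 12mL/hr for the first infusion or 25mL/hr for subsequent infusions". It makes no exception for a subsequent infusion that was begun at 12 mL/hr.

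Section 6.4.6 asks for special caution "during the infusion for any subject who did not tolerate a previous infusion well", limits how far and how soon the rate may be raised after an interruption, and sends the reader back to the rules above: "See Section 5.1.1.3 for details on management related to intensity of adverse events".

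**The concern.** The severe-reaction rule looks designed to return the subject to the start of the schedule in use: 12 mL/hr for Table 2, 25 mL/hr for Table 3. Because it is keyed to infusion number, it does this for the first infusion and for subsequent infusions on Table 3. It does not do so for a subsequent infusion on Table 2. The subjects left out have already reacted severely and were given a slower start for that reason, and for them the severe rule can be less cautious than the mild one.

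What is at stake is safety during the infusion. The case also falls within the period of higher risk. Section 6.4.6 states that "Infusion reactions occur more frequently with the first 2 infusions", and the second infusion counts as a subsequent one, so a severe reaction to the first dose puts the second on the 12 mL/hr start. Subsequent infusions are also more concentrated than the first: 1 mg/mL against 0.3 mg/mL (Section 5.1.1).

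**Working it through.** **Inputs.** Table 2 rates: 12, 25, 50, 100, 200, 300 and 400 mL/hr. Table 3 rates: 25, 50, 100, 200 and 400 mL/hr. Each step before the last takes 30 minutes (Section 5.1.1.2). Volume is 1000 mL (Section 5.1.1). The restart rules are those of Sections 5.1.1.3.1 and 5.1.1.3.2.

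**The plan's own durations, to confirm that the tables are read correctly.**
- Table 2: the first six steps deliver (12 + 25 + 50 + 100 + 200 + 300) × 0.5 = 343.5 mL in 3 h. The remaining 656.5 mL at 400 mL/hr takes 1.64 h. Total 4.64 h; the protocol says approximately 4.5 h.
- Table 3: the first four steps deliver (25 + 50 + 100 + 200) × 0.5 = 187.5 mL in 2 h. The remaining 812.5 mL at 400 mL/hr takes 2.03 h. Total 4.03 h; the protocol says approximately 4 h.

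**Restart rate on a subsequent infusion that was started at 12 mL/hr on Table 2.** Grade 1–2 rule: half the rate at the pause, or 12 if paused at 12. Grade 3 or higher rule: 25 at every pause rate.

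| Rate at pause (mL/hr) | Grade 1–2 restart | Grade ≥3 restart | Severe ÷ mild | Severe ÷ rate at pause |
|---|---|---|---|---|
| 12 | 12 | 25 | 2.08 | 2.08 |
| 25 | 12.5 | 25 | 2.0 | 1.0 |
| 50 | 25 | 25 | 1.0 | 0.5 |
| 100 | 50 | 25 | 0.5 | 0.25 |
| 200 | 100 | 25 | 0.25 | 0.125 |
| 300 | 150 | 25 | 0.17 | 0.08 |
| 400 | 200 | 25 | 0.125 | 0.06 |

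Only a pause at 12 mL/hr gives a restart faster than the rate at which the reaction occurred. At 1 mg/mL this is a move from 12 to 25 mg/hr. It follows at most 12 mL/hr × 0.5 h = 6 mL, or 6 mg, if the pause falls in the first step of the table.

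**How often the rule can act.** Section 5.1.1.3.2 calls for withdrawal when the same event reaches grade 3 three times in one infusion, so the restart rule can apply twice within one infusion.

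**The case against.** The strongest reply is that the protocol does not plainly order a faster restart. Several provisions could hold the rate down.

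- *The cap in Section 6.4.6.* An increase after an interruption may not exceed the scheduled amount: no more than a doubling, and no sooner than every 30 minutes. If 12 to 25 across a pause counts as such an increase, the time limit would bar it for a reaction in the first half hour, and 25/12 = 2.08 is slightly more than a doubling. But the cap is defined by Tables 2 and 3, and 12 to 25 is itself a scheduled Table 2 step. The matching limit in Section 5.1.1.3.2 governs increases made after the restart. At a pause of 25 mL/hr there is no increase to cap. The cap makes the text ambiguous; it does not clearly displace the fixed rate.
- *The safety exception in Section 5.1.1.2.* Modifications are "not permitted with the exception of those initiated for patient safety (i.e. due to infusion reactions"). A site could rely on this to go slower, but it gives no rate and would be set against an explicit requirement.
- *Other safeguards.* The infusion has been stopped and the event treated, restarting is optional, withdrawal rules apply, and steroid premedication may be reduced only if the second infusion was free of severe events. These stand and lower the risk. None sets the restart rate.
- *The Study Procedures Manual.* Section 5.1 refers to it for handling of infusion reactions. It was not available and may cover this case.

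Two wider readings are tempting but not supported. A reader might infer that the missing reduction at 25 mL/hr is a fault on every subsequent infusion. On a Table 3 infusion, 25 mL/hr is the starting rate, so the rule returns the subject to the start of the schedule, just as a first infusion paused at 12 restarts at 12.

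A reader might also see a conflict within the first infusion, because Section 5.1.1.2 says, with no grade limit, "If an infusion reaction develops, the infusion should be temporarily slowed or interrupted. Upon restart, the infusion rate should be half" of the rate at the pause. That sentence is general and advisory. Section 5.1.1.3.2 is specific to grade 3 or higher and mandatory, and Section 6.4.6 points to Section 5.1.1.3 for management by intensity. The specific rule governs.

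**Conclusion.** The gap is real but narrow and minor. It concerns only subsequent infusions begun at 12 mL/hr on Table 2, and only when a further grade 3 or higher reaction occurs at 12 or 25 mL/hr and the investigator restarts.

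The conclusion rests on a literal reading of the fixed rate in Section 5.1.1.3.2 and on the manual not supplying an exception. Frequency cannot be derived from the documents and is probably low: it takes a severe reaction at one infusion, continued treatment, and another severe reaction at one of the two lowest rates of the next. Section 3.2 also notes that adverse events in earlier ofatumumab trials were mainly infusion-related events on the day of the first infusion. No endpoint, analysis population or error rate is affected.

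**What to change.** Amend the restart sentence in Section 5.1.1.3.2 so that the rate is 12 mL/hr for the first infusion and for any subsequent infusion started at 12 mL/hr under Table 2, or 25 mL/hr for other subsequent infusions. Make the same change in the Study Procedures Manual if it repeats the rule. Table 3 infusions are unchanged.

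The cost is the wording and one extra 30-minute step for a few subjects. That step delivers 6 mL, which would otherwise take 6/400 h = 0.9 minutes at the top rate, so the net delay is 30 − 0.9 = 29.1 minutes for each restart.

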5.2. Treatment Assignment

Subjects will be assigned to study treatment in accordance with the randomization schedule (see Section 3.1.2). Please refer to the SPM for detailed instruction.

5.3. Product Accountability

In accordance with local regulatory requirements, the investigator, designated site staff, or head of the medical institution (where applicable) must document the amount of investigational product dispensed and/or administered to study subjects, the amount returned by study subjects, and the amount received from and returned to Novartis, when applicable. Product accountability records must be maintained throughout the course of the study.

5.4. Prohibited Concomitant Medication or Therapies

- Anti-cancer medication not part of the protocol treatment (e.g. alkylating agents, anti-metabolites, purine analogues, other monoclonal antibodies, and other medications including glucocorticoids)
- Any non-marketed drug substance or experimental therapy

Note: Glucocorticoids given for other indications such as exacerbations of asthma or as premedication for ofatumumab infusions are allowed.

6. STUDY ASSESSMENTS AND PROCEDURES

Please refer to Appendix 1 Time and Events

6.1. Clinical Assessments

6.1.1. Demographics

At screening, date of birth, sex, and race/ethnicity is collected.

6.1.2. Disease Characteristics and Medical History

At screening, relevant medical history is collected including:

- Date of initial CLL diagnosis
- Rai and Binet staging at diagnosis and screening
- Listing of relevant past and current diseases

6.1.3. Previous CLL Therapy

Prior treatment of CLL will be recorded including name of therapy, start and end date, dosing information, response and duration of response.

6.1.4. Height and Weight

Height (without shoes) will be measured at screening and recorded in the eCRF. Body weight (without shoes) will be measured at screening and throughout treatment and follow-up phases and recorded on the eCRF.

6.1.5. Physical Examination

A general physical examination is required at the screening visit and at visits during the study. This physical will include general appearance including examination of the following: skin, palpation of the lymph nodes, extremities, abdomen including determination of hepatomegaly, respiratory, cardiovascular, musculoskeletal, and neurological systems.

6.1.6. Electrocardiogram

A standard 12-lead electrocardiogram (ECG) is required at screening. The investigator will perform an overall interpretation of the ECG or may delegate this task to a cardiologist, if applicable. Additional ECGs may be obtained as clinically warranted at the discretion of the PI or delegate.

6.1.7. Vital Signs

Vital signs including temperature, blood pressure (BP), and pulse are documented per Appendix 1 Time and Events and during ofatumumab intravenous infusions. Temperatures for individual subjects must be measured using the same method at all visits.

6.1.8. Concomitant Medication

Any medication other than the trial drug is considered concomitant medication (apart from protocol defined premedication given prior to the infusions of ofatumumab) and will be documented, including the following information:

- Indication

- Dose information
- Start date
- Stop date of administration or ongoing at study termination

Of note: Intravenous gamma globulin, prophylactic antibiotics, and G-CSF may be given per local standard of care, at the physician's discretion.

6.1.9. ECOG Performance Status

An Eastern Cooperative Oncology Group (ECOG) Performance Status value is required at screening and throughout treatment and follow-up phases, to evaluate daily living abilities. Please refer to SPM for definitions of the ECOG performance status.

6.1.10. Constitutional Symptoms (B-Symptoms)

Assessment for the presence of the following symptoms will be performed at screening and at each visit:

- night sweats without signs of infection
- unintentional weight loss $\geq 10\%$ within the previous 6 months
- recurrent, unexplained fever of greater than 100.5°F for 2 weeks without signs of infection
- extreme fatigue

6.1.11. Lymph Node and Organ Examination

A physical lymph node and organ (spleen and liver) examination will be performed at screening and throughout the trial as part of disease status assessment.

Lymph nodes evaluation requires physical exam recording the diameter in two planes of the largest palpable node in each of the following sites: cervical, axillary, supraclavicular, inguinal and femoral. Lymphadenopathy is defined as lymph nodes with the largest diameter greater than 1.5 cm.

Liver and spleen size is assessed by physical exam and documented as 'cm' under the costal margin.

6.1.12. Pre-treatment Computed Tomography (CT) Scans

All subjects must have a CT scan with contrast of the thorax, abdomen, and pelvis performed at screening to confirm remission status. CT scans performed within 6 weeks prior to entering the study and collected according to defined standards can be used as screening CT scans. Clinical staging is independent of CT scan results.

